**Table 2 Events Ending Follow-up and Censoring Variables**

		Operational Definition
Events ending follow-up, throughout the follow-up		
1	End of 24-month follow-up	2 years from end of initiation grace period for each patient
2	Death	For THIN Italy and Belgium: last contact date, which defines exit from the database regardless of reason (death, physician change, or choosing to exit the database) For Inspur China: Date of death directly available by a report from social security sent to Inspur
3	Loss to follow-up/exit of data source	For THIN Italy and Belgium: last contact date, which defines exit from the database regardless of reason (death, physician change, or choosing to exit the database) For Inspur China: Date of lost to follow-up, which defines exit from the database regardless of reason (death or migration to another city)
Censoring during follow-up, after the 30-day initiation grace period: deviation from the assigned treatment strategy		
1.1	OM-85 group: None	-
1.2	SOC/non-user group: at first date of OM-85 prescription during follow-up (after the initiation grace period)	Same
1.3	Sensitivity analysis: The SOC/non-user group are censored at the first date of prescription for any bacterial lysate (including OM-85), the OM-85 group would be censored at the first date of prescription of any bacterial lysate other than OM-85 during follow-up	Same

Note: CED: cohort entry date; SOC: standard of care; THIN: The Health Improvement Network.

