**CCI**

**CCI**

**CCI**

**CCI**

**CCI** The dates provided in [Table 5](#) applies to the Tianjin Province.

 While these subgroups are formed based on OM-85 treatment cycle length and number, the analyses shall be reported with caution because patients who had data available for longer (e.g., longer cycle length) may represented a healthier population, as they had survived longer than the ones with shorter length.

 If few patients have a treatment cycle length of exactly 90 days, this category may be collapsed with the first category.

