Comparative analysis comparing outcomes measured before and after OM-85 initiation will be performed in all patients assigned to OM-85 exposure group. The distribution of the outcomes measured before and after OM-85 initiation (including various follow-up windows per specified in each objective) will be presented. Generalised linear models will be used, with the flag that indicates before or after OM-85 initiation as the independent variable and the outcome of interest as dependent variable.

Comparative analysis comparing the two exposure groups (treatment strategies, i.e., OM-85, or SOC/non-user) will be performed among the PS-matched samples. The distribution of the outcomes measured in each exposure group and in various follow-up windows as specified in each objective will be presented. Generalised linear models will be used, with the flag that indicates exposure group assignment (i.e., OM-85 or SOC/non-user) as the independent variable and the outcome of interest as dependent variable.

For all the generalised linear models used, distribution and link functions that are appropriate to the type of outcome will be used. Offset will be applied when applicable. Estimated coefficients (or corresponding exponentiated estimates, e.g., IRR) of the independent variables with corresponding 95% CI and significance level (i.e., p-value) will be reported. Cluster-robust standard errors will be used in estimating CI and significance level, to account for correlated data.

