### **3.7.3 Analysis of Primary Endpoint: RTI Rates (Primary Objectives 1-2, Secondary Objectives 3-4, Exploratory Objectives CCI)**

The primary outcome is the rate of RTIs episodes measured during different periods of interest, as specified in the objectives. The rate of RTI episodes will be estimated by calculating the total number of RTI episodes observed, divided by the total number of person-time (e.g., person-years) during a period of interest. Rates of RTI episodes will be estimated separately in patients initiating preventive treatment with OM-85 and in the SOC/non-user group. Furthermore, rates of RTI episodes during the baseline period will serve as reference in each treatment group to evaluate the effects of therapy during follow-up.

Comparative analysis comparing the RTI rates before and after OM-85 initiation, and analysis comparing RTI rates in the two exposure groups will be performed using approaches as described in the General Considerations. Generalised linear models with a Poisson distribution or negative binomial distribution (to account for over-dispersion) will be used to estimate the association between the initiation of OM-85 and the outcome of RTI rates, with the natural logarithm of the time at risk as offset (42).

The analyses will be identical for the exploratory objectives **CCI** **CCI** (Section 3.2.2.3).

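### The before-after model uses the patient only for the standard error, so database exit related to RTI risk shifts the rate ratio for an inert drug, in either direction

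*Protocol*

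**What the plan says.** Section 3.7.1 states that the before-after comparison "will be performed in all patients assigned to OM-85 exposure group", and gives its form: "Generalised linear models will be used, with the flag that indicates before or after OM-85 initiation as the independent variable". On dependence within patients it says: "Cluster-robust standard errors will be used in estimating CI and significance level, to account for correlated data". No patient stratum, patient effect or censoring weight is specified.

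Section 3.7.3 defines the rate as total episodes "divided by the total number of person-time (e.g., person-years) during a period of interest". It chooses a Poisson or negative binomial distribution, "with the natural logarithm of the time at risk as offset".

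Section 3.1.1 secures at least 12 months of baseline data for every patient. The after period runs to 24 months at most and can end earlier (Table 2). In the THIN databases, death and loss to follow-up are both dated by the "last contact date, which defines exit from the database regardless of reason (death, physician change, or choosing to exit the database"). No minimum follow-up is required.

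**The concern.** The before rate gives every initiator the same weight, one year each. The after rate weights each initiator by the time observed. The two rates describe the same patient mix only if observed time is unrelated to RTI risk. If it is related, the ratio moves although no patient's own rate has changed. Cluster-robust errors alter the interval and the p-value, not the estimate.

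This affects one of the two primary effectiveness contrasts. It grows with the length of the window, and 24 months is a primary window (section 2.1). Section 3.9.1.1 lists disease progression, access to care and infection rates as threats to the before-after comparison, but not differential exit.

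**Working it through.** **1. The plan's own figure.** Section 3.5 uses 2 episodes per person-year at baseline, equal person-time and an F-based interval. With 350 person-years and IRR 0.9, b = 2 × 350 = 700 and a = 0.9 × 700 = 630. The 95% CI width is 0.197, as in Table 9, against 0.213 at 300 person-years. All 32 cells of the table reproduce to within 0.0005. The sizing is not in error. It supplies the baseline rate used below and a yardstick: the protocol calls an IRR of 0.9 a small effect.

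**2. What the planned model estimates.** With a flag and a log-time offset only, the Poisson estimate is

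IRR = (Σ after-episodes / Σ tᵢ) / (Σ before-episodes / n),

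where tᵢ is patient i's observed after time in years and each before period is one year. For an inert drug and a constant personal rate λᵢ, this tends to

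[Σ λᵢtᵢ / Σ tᵢ] / mean(λ) = 1 + Cov(λ, t) / [mean(λ) · mean(t)].

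It equals 1 only if λ and t are uncorrelated. The sign of the shift is the sign of the covariance.

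**3. Size.** The risk spread and exit rates are assumptions, because the protocol gives neither. Half the patients have 1 RTI a year and half have 3 (mean 2, as in section 3.5). Annual exit probability d gives hazard h = −ln(1 − d) and mean observed time (1 − e^(−hT))/h over a window of T years.

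For 10% (low risk) and 30% (high risk) with T = 2:
- hazards are 0.1054 and 0.3567, and mean observed times are 1.8033 and 1.4299 years;
- the after rate is (1 × 1.8033 + 3 × 1.4299) / (1.8033 + 1.4299) = 1.8845;
- the IRR is 1.8845 / 2 = 0.942.

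| Annual exit, low / high risk | Null IRR, 12 months | Null IRR, 24 months |
|---|---|---|
| 5% / 5% | 1.000 | 1.000 |
| 2% / 5% | 0.996 | 0.992 |
| 5% / 10% | 0.993 | 0.987 |
| 5% / 15% | 0.986 | 0.973 |
| 10% / 30% | 0.970 | 0.942 |
| 30% / 10% (reverse) | 1.030 | 1.058 |

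I also tried gamma-distributed risk (mean 2, relative variance 0.5 and 1, exit split at the median). At 24 months this gave 0.939 and 0.920 for 10%/30%, and 1.061 and 1.080 for the reverse. Under negative binomial (simulated, dispersion fixed at 0.25, two risk classes), the 24-month values were 0.979 for 5%/15% and 0.954 to 0.956 for 10%/30%.

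**4. The conditional model.** Conditioning on the patient, the ratio r solves

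Σ [after-episodesᵢ − Nᵢ · r·tᵢ / (1 + r·tᵢ)] = 0,

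where Nᵢ is the patient's total over both periods. If tᵢ = T for everyone, then r = Σ after / (T · Σ before), which is exactly the planned Poisson estimate. The two differ only when follow-up differs.

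**5. With the eligibility rule applied.** Table 4 requires at least one RTI in the baseline year. Without any loss, the two-class example then gives:
- probability of at least one baseline RTI: 1 − e⁻¹ = 0.6321 and 1 − e⁻³ = 0.9502;
- before rate: (1 + 3) / (0.6321 + 0.9502) = 2.528;
- after rate: (0.6321 + 3 × 0.9502) / 1.5823 = 2.201;
- ratio 0.87 for an inert drug, which is regression to the mean and not an effect of exit.

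Simulation at 24 months (2,000,000 patients per scenario before selection, two risk classes, inert drug):

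| Annual exit, low / high risk | Planned Poisson | Conditional Poisson |
|---|---|---|
| none | 0.870 | 0.870 |
| 5% / 15% | 0.851 | 0.867 |
| 10% / 30% | 0.825 | 0.861 |
| 30% / 10% | 0.913 | 0.879 |

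Exit moves the planned estimate by up to 0.045 and the conditional one by up to 0.009. The starting value of 0.87 is common to both. Without the eligibility rule, the conditional estimate stayed between 0.998 and 1.002.

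**The case against.** A marginal rate ratio with cluster-robust errors is a standard before-after analysis. Section 3.7 leaves detail to the SAP, and section 3.9.1.1 already asks for cautious interpretation. Section 3.9.5 reports that the feasibility assessment found no significant loss at the selected time points. The point about size stands: on that expectation the shift is well inside the protocol's own small effect. The other points do not settle the matter, because the protocol states the model form itself and no listed caution covers differential exit.

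Four stronger readings are tempting, and the documents do not support them.

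- **That the shift favours OM-85.** No section says that higher-risk initiators leave earlier. Physician change and choosing to exit have no stated link to RTI risk. A last-contact date may truncate patients who seldom consult, and that pushes the ratio above 1.
- **That the protocol admits the problem.** Table 5, footnote 3 says "patients who had data available for longer (e.g., longer cycle length) may represented a healthier population", but it concerns subgroups formed by OM-85 cycle length and number. It does not say that patients who exit have more RTIs.
- **That exit is known to be heavy.** Average follow-up of 9 and 7 years (section 3.4.1) would give 1 − e^(−2/9) = 20% and 1 − e^(−2/7) = 25% exit in 24 months under a constant hazard. Those averages cover all database patients, not initiators with at least a year of enrolment, and they include follow-up cut off only by the end of the data.
- **That exit alone would often give a significant result for an inert drug.** Any such frequency needs an exit share and a cohort size. The first is not given, and sections 3.5 and 3.9.5 say that fewer initiators will be included than the feasibility counts.

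**Conclusion.** The point holds conditionally. As written, the before-after estimate is shifted whenever database exit is related to RTI risk, and the robust standard error does not correct this. The direction cannot be determined from the protocol.

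The size rests on assumed exit rates and an assumed spread of risk. It is about 0 to 3% if loss is as low as section 3.9.5 expects, and about 4 to 8% at 24 months under Poisson with 10% versus 30% annual exit. It is somewhat less under negative binomial and about half at 12 months. This is a modest flaw in a primary contrast. It merits a change because the remedy costs almost nothing, not because a large bias has been shown.

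**What to change.** For primary objective 1 and secondary objective 3, fit a Poisson model conditional on the patient: patient as stratum, before/after flag, log time as offset, robust standard errors. Beside the plain before rate, show it weighted by each patient's after time, Σ(before-episodesᵢ · tᵢ)/Σtᵢ, so that the displayed rates refer to the same mix. Reporting the share who exit by each time point, by number of baseline RTIs, would show the direction and likely size of the shift.

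The cost is one model statement in standard software. Initiators must have a baseline RTI, so essentially all remain informative.

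The protocol or SAP should state the limits. The conditional model deals essentially only with differential exit. It does not remove regression to the mean from requiring a baseline RTI and entering at an RTI, nor exit caused by an RTI during follow-up. The text should not imply that the model returns 1.00 for an inert drug.

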### **3.7.2 Analysis Population(s)**

The number and percentage of patients selected into the overall study population, by meeting all the inclusion criteria (no exclusion criteria applied), will be presented for each data source (country), and separated by exposure group. This will be done before and after applying the PS matching.

The analysis populations for each objective are defined in [Section 3.2.2](#).

Of note, when complete case analysis is used to handle missingness, the number of patients contributing to each analysis depends on the availability of the necessary data within the data sources; therefore, the population size may significantly vary between study objectives.

### **3.7.3 Analysis of Primary Endpoint: RTI Rates (Primary Objectives 1-2, Secondary Objectives 3-4, Exploratory Objectives CCI)**

The primary outcome is the rate of RTIs episodes measured during different periods of interest, as specified in the objectives. The rate of RTI episodes will be estimated by calculating the total number of RTI episodes observed, divided by the total number of person-time (e.g., person-years) during a period of interest. Rates of RTI episodes will be estimated separately in patients initiating preventive treatment with OM-85 and in the SOC/non-user group. Furthermore, rates of RTI episodes during the baseline period will serve as reference in each treatment group to evaluate the effects of therapy during follow-up.

Comparative analysis comparing the RTI rates before and after OM-85 initiation, and analysis comparing RTI rates in the two exposure groups will be performed using approaches as described in the General Considerations. Generalised linear models with a Poisson distribution or negative binomial distribution (to account for over-dispersion) will be used to estimate the association between the initiation of OM-85 and the outcome of RTI rates, with the natural logarithm of the time at risk as offset (42).

The analyses will be identical for the exploratory objectives **CCI** **CCI** (Section 3.2.2.3).

### 3.7.4 Analysis of Other Secondary Endpoint(s)

#### 3.7.4.1 Baseline Characteristics (Secondary Objective 1)

Patient demographics, type of previous RTI episodes (URTI, LRTI, Other), comedications, antibiotic use (number of prescriptions, types, duration of treatment), comorbidities and healthcare resource utilisation during baseline will be described using descriptive statistics appropriate to the variable type.

#### 3.7.4.2 Prescribing Pattern of OM-85, Antibiotics and Concomitant Medications of Interest (Secondary Objectives 2, 5, 6, and Exploratory Objectives **CCI**)

For prescribing pattern of OM-85, antibiotics, and other concomitant medications of interest, the number of prescriptions and duration of use of medications of interest will be summarised with descriptive statistics as continuous variables. Dosage level of OM-85 prescription will be described as categorical variable. Categorical variables will be summarised using frequency tables (frequencies and percentages).

**CCI**  
**CCI**  
**CCI**  
**CCI**

#### 3.7.4.3 Healthcare Visits (Secondary Objective 7, and Exploratory Objectives **CCI**)

The number and proportion of patients with each type of visit will be reported. Among those with each type of visit, total number of visits, and length of hospitalisations (when applicable) will be reported. Annualised rate expressed by person-years will be calculated.

**CCI**  
**CCI**  
**CCI**  
**CCI**

### 3.7.5 Analysis of Other Exploratory Endpoints

#### 3.7.5.1 [CCI] (Exploratory Objectives [CCI])

[CCI]  
[CCI]  
[CCI]  
[CCI]

#### 3.7.5.2 [CCI] (Exploratory Objective [CCI])

[CCI]  
[CCI]  
[CCI]  
[CCI]  
[CCI]  
[CCI]

### 3.7.6 Subgroup Analyses and Stratifications

Planned subgroup analyses and stratifications are described in [Section 3.2.2.3](#) and will be further detailed in the SAP.

### 3.7.7 Sensitivity Analyses

The sensitivity analyses will be applied to primary objectives and will be detailed in the SAP. At minimum, the following will be considered:

[figure not shown]
- **Varying maximum length of an RTI episode, for primary outcome definition:** The length of an RTI episode (14 days) will be altered in sensitivity analysis using 7 days and 21 days. The results will inform the robustness for the definition in the main analysis.
- **Censoring at initiation of other bacterial lysates than OM-85:** In both exposure groups, patients are censored at date of the first prescription of another bacterial lysate.

In addition, for primary objective 2, sensitivity analysis will be conducted **implementing clone censor weighting methods on the total population to account for potential immortal time bias and selection bias.** In place of PS matching to set up the study cohort, per protocol analysis implementing methods of clone censor weighting will be implemented. In this method, all patients will be included, not only those that are matched in PS matching, and follow-up will begin at CED. To explain further, at CED, each patient will be cloned and assigned to both an exposed and unexposed (one for each clone) and therefore each patient will have been assigned all treatment strategies at CED or time zero of follow-up. Each clone is then followed during the

30-day initiation grace period. Patients will be censored from the cloned OM-85 exposed group at the end of the 30-day initiation grace period, if no prescription of OM-85 is observed by then. Patients will be censored from the cloned SOC/non-user group, if a prescription of OM85 is observed during the 30-day initiation grace period (censoring at the date of the prescription). Artificial censoring of the clones when they deviate from their treatment assignment could create potential selection bias due to informative censoring, and thereby inverse probability weighting will be applied to adjust for potential risk of informative censoring, after the CED. The weights are implemented, because not receiving an OM-85 prescription during the 30-day initiation grace period (and thus being censored) is likely not at random, but influenced by variables that could also impact the outcome (confounders) (37). The censoring weighs up the influence of the patients who remain uncensored to account for similar patients who were censored, breaking the association between censoring and variables that may cause the outcome. The variables included in the weighting can include baseline variables and time-varying confounding variables that could change during the 30-day initiation grace period, such as healthcare resource utilisation (e.g. hospitalisation) or receiving a diagnosis of a respiratory condition. Description of baseline as well time-varying variable that change during the initiation grace period will be described and compared in user and non-user groups. The time-varying variables will be selected from the list of baseline factors (as listed above for PS), but they are measured also after CED. These variables will be further defined in the SAP. The cloning and censoring are illustrated in [Figure 3](#).

